4. METHODS

4.1 Study design

A nested case-control analysis in a retrospective cohort study will be performed using The Health Improvement Network (THIN) database in the UK. Data is prospectively recorded by participating primary care physicians as part of their routine patient care (see 4.2).

A nested case-control analysis will be conducted comparing incident cases of seizure versus controls selected with incidence density sampling. A graphical presentation of the study design is provided in Figure 1.

The rationale of our study design is:

- 1) to enhance the internal validity of users of acid-suppressing drugs by ascertaining individuals newly prescribed acid-suppressing drugs.
- 2) to maximize the power to quantify the risk of seizure associated with current use of acid-suppressing drugs by including all the experience available of acid-suppressing users.

4.2 Source population

THIN is a computerized medical research database that contains systematically recorded data on more than 3 million UK primary care patients. It is representative of this population with regard to age, sex, and geographic distribution, and has been validated for use in pharmacoepidemiological research in multiple studies (Lewis et al 2007). Participating primary care practitioners (PCPs) record data as part of their routine patient

care, including demographics and life style factors (e.g. alcohol use, body mass index (BMI) and smoking status), consultation rates, referrals, hospital admissions, laboratory test results, diagnoses, prescriptions ordered by the PCPs, and a free text section, and send their data anonymously to THIN for use in research projects. Prescriptions issued by PCPs are recorded automatically in the database. The Read classification is used to code specific diagnoses (Stuart-Buttle et al 1996), and a drug dictionary based on data from the MULTILEX classification is used to code drug prescriptions (First Data Bank 2010).

The rationale for selection of THIN is the unique attributes of primary care databases in the UK (e.g. GPRD, Qresearch) for pharmacoepidemiological research. As GPRD and THIN are basically equivalent, we chose the database our research group has greater experience.

4.3 Study population

THIN will be used to identify all individuals aged 20–84 years from 1 January 2005 to 31 December 2011, who have been enrolled with their PCP for at least 2 years and have a computerized prescription history of at least 1 year. Patients will have to be free of acid-suppressing drugs (PPI or H₂RAs) for at least one year, and never have a diagnosis of cancer, alcohol abuse or alcohol-related disease, or drug abuse. When an individual meet all these eligibility criteria that date will be marked as start date. Patients aged ≥ 70 years with a follow-up longer than 1 year will be excluded from the study population if they have fewer than two recorded consultations with a PCP during their entire follow-up (proxy for incomplete and invalid data recording). All remaining individuals will constitute the final study population.

4.3.1 Eligibility criteria

To be included in the study, patients must meet all of the following criteria at start date:

- At least 2 years of registration with the PCP
- At least 1 year of computerized prescription history
- Age 20-84 years

4.3.2 Exclusion criteria

All patients fulfilling one of the following criteria will be excluded:

- Patients with at least 1 prescription of PPI or H₂RA in the year prior to start date
- Cancer before start date
- Alcohol abuse or alcohol-related disease before start date
- Drug abuse before start date
- Patients aged ≥ 70 years with a follow-up after start date longer than 1 year and fewer than 2 recorded consultations with a PCP during their entire follow-up

4.4 Follow-up

All members of the study cohort will be followed up from the day after start date until the first occurrence of the following endpoints:

- First recorded entry of seizure (Table 2)
- Age = 85 years
- Cancer
- Alcohol abuse or alcohol-related disease
- Drug abuse
- End of the study period

4.5 Outcome definition and ascertainment

Free text comments will be requested before reviewing patient profiles. Information will include demographic data and all clinical information. The profiles of computer detected patients with seizure/convulsion (Table 2) identified with the initial computer search and including free-text comments, will be reviewed manually to ascertain the number of potential cases with an incident episode of seizure. All patient personal identifiers will be suppressed and information on drug use removed to allow for a blinded revision of patient profiles. The date of onset of study outcome will be used as index date. Doubtful cases will be reviewed by two MD researchers and agreement will be reached. Patients will not be retained as seizure cases if they were admitted to hospital in the month before the index date; in-patient drug exposure is not available and therefore recent exposure in these patients would be unknown. All patients meeting our operational definition of seizure (see below) will be considered potential cases.

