4.6 Selection of Controls

A random series of controls, calendar-year-frequency matched to seizure cases will be sampled from the pooled study cohorts. This will be done by generating a random date within the study period for each study member. If the random date for a study member is included in the follow-up period, that person will be marked as an eligible control and the random date will be used as their index date. This method of selection of controls in nested case-control studies is known as "incidence density" sampling. The final size of the control sample will be determined by being at least four times the size of the final list of cases and be a round number.

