4.7 Characterization and assessment of risk factors

The following potential confounders and/or effect modifiers will be ascertained:

Demographics; Age at index date (20-39, 40-49, 50-64, 65-74 and 75-84 years), sex and calendar year of index date (2005-2006, 2007-2008 and 2009-2011). We will also calculate the time interval between start date and index date and subsequently categorize it into 5 time periods: first month; 2 to 6 months; 7 to 12 months; 1 to 2 years and longer than 2 years. This variable can be considered as adjustment/proxy for time to event. Socioeconomic status will be computed with the Townsend score.

Life style factors; Body mass index (calculated from recorded height and weight; weight in kg / (height in metres²) will be ascertained prior to index date. Standard cut points used to classify subjects are: underweight (BMI less than 20), normal weight (BMI 20-25), overweight (BMI 25 to 29) and obese (BMI \geq 30 kg/m²). Smoking status will be categorized into current smoker, past smoker, never smoker. Missing data will be assessed as a separate category. Most recent value before index date will be ascertained.

Comorbidity; Diabetes, coronary heart disease (MI, unstable angina or angina), cerebrovascular disease (ischaemic or haemorrhagic), epilepsy, seizure, COPD, GERD, and peptic ulcer antecedents (which includes dyspepsia, gastritis, uncomplicated peptic ulcer and complicated peptic ulcer), bipolar disorder, anxiety, depression, neuralgia/neuralgic pain, polyneuropathy/peripheral neuropathy, migraine, autoimmune disorders, CNS infections, cerebral trauma, hypertensive encephalopathy, eclampsia, mental retardation, cerebral palsy, dementia. Comorbidity will be ascertained prior to index date.

Comedication; Antiepileptic drugs, anxiolytics, hypnotics, antibiotics, antihypertensives (e.g. diuretics, beta-blockers...), antihistamines, antidepressants, statins, antidiabetics, nitrates, clopidogrel, low-dose ASA, NSAIDs, oral corticosteroids, oral anticoagulants. We will also collect information on polypharmacy: number of prescribed different drugs in the 30 days prior to the index date (0, 1-2, 3-5, 6-9, 10 or more). Comedication will be ascertained prior to index date.

Health care utilization: Number of GP visits, referrals and hospitalizations the year prior to index date.

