4.9 Statistical analysis

Incidence rate of seizure overall as well as age and sex-specific will be computed in the study cohort.

A nested case-control analysis will be performed to assess the effect of acid-suppressing drugs and potential risk factors for seizure using unconditional logistic regression. In this analysis all patients ascertained with an incident episode of seizures will be used as

cases. The control group will comprise a random sample of study cohort members, frequency-matched by calendar year (described in section 4.6). Under our study design of incidence density sampling, the odds ratio (OR) is an unbiased estimator of the incidence rate ratio (RR) (Rothman 2002).

To determine the association between study outcome and current use of PPI and H₂RA, we will run unconditional logistic regression models and compute the OR and their 95% confidence intervals (95%CI). The estimates will be adjusted for the frequency-matched variable (calendar year), age, sex, time to event and other independent risk factors described in section 4.7.

Sub-analyses will be repeated in the strata of individuals with epilepsy and individuals free of epilepsy for descriptive purposes.

Statistical analyses will be performed using Stata package version 11.0 (StataCorp LP, College Station, TX, USA).

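### Recently hospitalised cases are dropped but recently hospitalised controls are kept, so the OR is not unbiased for the rate ratio as claimed; the PPI and H2RA ORs may be shifted, most likely downward if recently admitted people have higher recorded use

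*Protocol*

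**What the plan says.** Section 4.5 restricts the cases: "Patients will not be retained as seizure cases if they were admitted to hospital in the month before the index date". The reason given is that "in-patient drug exposure is not available and therefore recent exposure in these patients would be unknown".

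Section 4.6 gives the whole eligibility test for controls: "If the random date for a study member is included in the follow-up period, that person will be marked as an eligible control". Section 4.9 repeats it in short form: "The control group will comprise a random sample of study cohort members, frequency-matched by calendar year". Neither section mentions a recent admission.

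Section 4.9, like the statistical analysis part of the synopsis, then relies on the sampling scheme for validity: "Under our study design of incidence density sampling, the odds ratio (OR) is an unbiased estimator of the incidence rate ratio (RR".

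The nearest covariate is in section 4.7 under health care utilization: "Number of GP visits, referrals and hospitalizations the year prior to index date".

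**The concern.** Incidence density sampling makes the OR estimate the rate ratio because controls are drawn from the person-time in which a case could have arisen and been counted. The rule in section 4.5 takes the month after any admission out of the case-producing person-time. Section 4.6 leaves that month in the person-time from which controls are drawn.

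The protocol's own reason for the exclusion does not distinguish the two groups. If in-patient supply is invisible, recent exposure is as uncertain for a control admitted a week before the random date as for a case. The plan treats exposure as unknowable in one group and classifies it as known in the other.

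At stake are the PPI and H2RA ORs of a drug safety study. If recently admitted people have more recorded acid suppression than others, keeping them only among the controls raises control exposure and lowers the ORs. Unlike random error, such a shift does not shrink as person-time accumulates.

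**Working it through.** **1. Where a matching rule could stand.**

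| Protocol section | What it governs | Recent admission |
|---|---|---|
| 4.3.2 | Exclusions tied to start date, and a low-consultation rule from age 70 | Not mentioned |
| 4.4 | Reasons for ending follow-up | Not among them |
| 4.5 | Cases | Removed if admitted in the prior month |
| 4.6 | Controls | Not mentioned; the random date need only fall in follow-up |
| 4.7 | Covariates | Hospitalisations counted over a year |
| 4.9 | Analysis | Not mentioned |

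The asymmetry is in the text and needs no assumption.

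**2. The plan's own precision figure (section 4.9.1).** 100,000 person-years × 50 per 100,000 = 50 events per group. SE(log RR) = √(1/50 + 1/50) = 0.20. Limits are exp(±1.96 × 0.20) = 0.68 and 1.48. The stated 1.48 reproduces and serves below as a rough yardstick.

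**3. Size in the crude OR.** The protocol gives no admission share and no exposure prevalence, so all inputs here are assumptions:
- p0: prevalence of recorded current PPI use without an admission in the prior month, set at 10%.
- p1: the same prevalence with such an admission.
- h: share of control index dates with such an admission.

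With a true OR of 1, retained cases have prevalence p0 and controls have pc = (1 − h)p0 + h·p1. The expected OR is [p0/(1 − p0)] / [pc/(1 − pc)]. This isolates the selection effect; confounding by admission is left out.

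| h | p1 | pc | Expected OR |
|---|---|---|---|
| 0.5% | 20% | 0.1005 | 0.994 |
| 1% | 20% | 0.101 | 0.989 |
| 1% | 30% | 0.102 | 0.978 |
| 2% | 30% | 0.104 | 0.957 |
| 3% | 40% | 0.109 | 0.908 |
| any | 10% | 0.100 | 1.000 |
| 1% | 7% | 0.0997 | 1.003 |
| 3% | 7% | 0.0991 | 1.010 |

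The same factor multiplies a non-null OR: at a true 1.5 the worst row gives 1.5 × 0.908 = 1.36.

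**4. After stratifying on any admission in the prior year.** Assumptions: 10% of cohort time has an admission in the prior year; 8-20% of that has one in the last month; prevalence is 10% with no admission and 20% with an earlier one; the case rate is 3 times higher in the admitted stratum; there are 4 controls per case. Example with a 10% last-month share and 30% prevalence in that month:
- Control prevalence in the admitted stratum: 0.9 × 0.20 + 0.1 × 0.30 = 0.21.
- Stratum OR: (0.20/0.80) / (0.21/0.79) = 0.94.
- Mantel-Haenszel OR over both strata: 0.98.

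Over last-month shares of 8-20% and last-month prevalences of 25-30%, the Mantel-Haenszel OR is about 0.97 to 0.99. With a last-month prevalence of 15% it is 1.01 to 1.02.

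**5. Dependence on the baseline.** With h = 3-5% and p1 = 25-40%, the crude factor is 0.82-0.94 if p0 = 8%, but 0.94-0.99 if p0 = 20%. For h = 5% and p1 = 40%: pc = 0.096 and the factor is 0.82 at p0 = 8%; pc = 0.21 and the factor is 0.94 at p0 = 20%.

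**6. With the exclusion on both sides.** h = 0 among controls, so pc = p0 and the expected OR is 1.00 whatever p1 is.

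**The case against.** The strongest reply concerns direction. A downward bias requires recently admitted controls to have higher recorded current use. Section 4.8 defines current use from the supply of the most recent prescription, and section 4.5 concedes that in-patient supply is not seen. A control treated from hospital stock may therefore appear as a recent user or non-user, which works the other way. A reader might infer that the ORs are biased downward as a matter of course; the protocol gives no prevalence that would establish this, and for H2RAs there is not even an assumed figure in the calculation. This objection stands.

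The second reply is that the planned estimate is adjusted. Section 4.7 lists comorbidity, polypharmacy in the prior 30 days and prior-year hospitalisations. This stands in part: adjustment shrinks the shift. It does not remove it, because a year's count does not isolate the excluded month, in which no retained case can fall.

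The third is size. The largest shift in the main range, ln 0.908 = −0.097, is about half the planning SE of 0.20. That is fair, but section 4.9.1 expects more person-time than it assumes. With four times as much, the SE would be √(1/200 + 1/200) = 0.10 and the same shift about one SE.

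A last reply is that the rule may be left to an analysis plan. It does not stand: section 4.6 is not silent but states an eligibility rule that admits these controls.

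**Conclusion.** The asymmetry is real, and the claim that the OR is unbiased for the rate ratio does not follow from the design as written. The consequence for the PPI and H2RA ORs is a possible bias, most likely downward if recently admitted people have higher recorded current use, and nil or slightly upward if their recorded use is equal or lower.

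Under assumed inputs (0.5-3% of control person-time with an admission in the prior month, 2-4 times a 10% PPI prevalence) the crude OR is multiplied by about 0.91-0.99. After stratifying on prior-year admission, about 0.97-0.99 remains when last-month prevalence is higher.

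A reader might infer a much larger effect, such as 0.82-0.94, in the oldest patients or in those with epilepsy, where admissions may be more frequent. That result needs an 8% baseline to be carried into those groups; with a 20% baseline the same admission shares give 0.94-0.99. The protocol supports neither baseline.

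This is a should-fix point: a wrong rule with a probably small effect of unsettled sign, and a correction that is nearly free.

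**What to change.** Add to section 4.6 that a sampled control is ineligible if admitted to hospital in the month before the random index date, and that replacements are drawn so that the condition "The final size of the control sample will be determined by being at least four times the size of the final list of cases" is still met. State in section 4.9 and in the synopsis that the OR then estimates the rate ratio in person-time without an admission in the prior month.

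If the incidence rates in section 4.9 use the same case list, also remove the person-time in the month after each admission from the denominator. Otherwise cases are dropped while their person-time stays, and the rates come out too low.

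The cost is one sentence and one filter at the control draw, plus a person-time adjustment if the case list is shared. Precision is not lost, because the controls are replaced. The change has to be made before the controls are drawn.

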4.5.1 Operational definition of incident case of seizure

A patient with an incident diagnosis of seizure during follow-up will be accepted as a case if the patient was referred to a consultant, and/or admitted to hospital for the event.

For the sub-analyses among patients with a diagnosis of epilepsy we will, however, also accept a broader case definition, i.e. an incident diagnostic code for a seizure during follow-up regardless of referral to specialist, or admission to hospital. The broader definition of seizure will be employed because we suspect that the threshold for seeking hospitalisation may differ between patients with epilepsy and non-epilepsy patients experiencing a seizure. Also, patients with epilepsy may already have attended specialist care when recruited into the cohort and will therefore not necessarily be referred to renewed specialist evaluation due to a further seizure in the follow-up period.

We will attempt to classify seizures into three categories:

- i. Acute symptomatic seizures:

Seizures occurring in close temporal relationship to one or more of the following:

CVD, traumatic brain injury, CNS-infection, severe systemic illness with fever, presenting symptom of multiple sclerosis (or within 7 days of relapse of this disorder), autoimmune diseases with signs of activation, metabolic causes (including hypoglycemia and low serum sodium), and cerebral hypoxia.

Close temporal relationship to the seizure is defined as 1 week for the majority of events listed, with certain exceptions. Longer intervals will be accepted in certain cases (e.g. subdural hematoma with no known trauma, cases of CNS-infection with signs of

persistent infection). Conversely, a shorter time-limit will be requested for hypoglycemia (24 hours). We will generally follow the recommendations of Beghi et al (2010) for the classification of acute symptomatic seizures.

ii. Unprovoked seizures:

Seizures not fulfilling the criteria for acute symptomatic seizures will be considered unprovoked seizures, if sufficiently documented with regard to the aforementioned possible causes of seizures listed under (i).

iii. Unclassifiable seizures:

Seizures with insufficient documentation to rule out acute symptomatic seizures.

Alcohol-related seizures or seizure in cancer patients will lead to exclusion.

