2. INTRODUCTION

A seizure is an abnormal, unregulated electrical discharge that occurs within the brain's cortical grey matter and transiently interrupts normal brain function. Due to the numerous properties that control neuronal excitability there are many different causes of seizures and epilepsy. In principal these relate to differences between individuals in the susceptibility or threshold of seizures (e.g. genetic factors), concomitant conditions with a high likelihood of leading to seizures (e.g. traumatic brain injury) and precipitating factors, intrinsic (e.g. psychological stress, sleep deprivation) and exogenous (e.g. certain medications) (Lowenstein 1998).

Seizures may be acute symptomatic or unprovoked. Acute symptomatic seizures are seizures occurring at the time of a systemic insult or in close temporal association with a documented brain insult. (Hauser and Beghi 2008). Unprovoked seizures are seizures occurring in the absence of precipitating factors and may be caused by a static injury (remote symptomatic seizures) or a progressing injury (progressive symptomatic seizures) (Hauser and Beghi 2008). The International League Against Epilepsy (ILAE) has defined epilepsy as “a disorder characterized by an enduring predisposition to generate epileptic seizures and by neurobiologic, cognitive, psychological and social consequences of this condition. This definition requires the occurrence of at least one epileptic seizure” (Fisher et al. 2005). The Commission on Epidemiology and Prognosis (1993) has recommended the use of the term acute symptomatic seizures as separate from the unprovoked seizures that define epilepsy in epidemiology studies (Beghi et al 2010).

The incidence of acute symptomatic seizures has been estimated to be 29–39 per 100,000 per year across several studies, regions and time periods. These predominate in men, in the youngest age class, and in the elderly (Hauser and Beghi 2008). Traumatic brain injury, cerebrovascular disease, drug withdrawal, and metabolic insults are the most common causes. In recent studies, the incidence of unprovoked seizures has been estimated to be 46-57 per 100,000 person-years. As with epilepsy, single unprovoked seizures predominate in men and in patients less than 12 months and older than 65 years (Hauser and Beghi 2008). Seizure etiology is the single most important risk factor for the increased mortality in patients with a first seizure (Hauser and Beghi 2008).

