3. STUDY OBJECTIVES

- To estimate the incidence of seizure in the general population and stratified by epilepsy status
- To estimate the relative risk of seizure associated with use of PPI and H₂RA and stratified by epilepsy status.

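### The prior-month admission rule in section 4.5 is justified only for the drug analysis, but as written it also removes cases from the incidence numerator and biases objective 1 downward

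*Protocol*

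**What the plan says.** Section 4.5 of the protocol puts a hospital-admission rule inside case ascertainment: "Patients will not be retained as seizure cases if they were admitted to hospital in the month before the index date". The reason follows directly: "in-patient drug exposure is not available and therefore recent exposure in these patients would be unknown". The rule covers an admission for any cause, and nothing confines it to the nested case-control analysis.

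Objective 1 in section 3 is "To estimate the incidence of seizure in the general population and stratified by epilepsy status". On how this will be done, section 4.9 says "Incidence rate of seizure overall as well as age and sex-specific will be computed in the study cohort". It names no case set for that rate other than the one that section 4.5 produces.

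Section 4.4 defines the time at risk: "All members of the study cohort will be followed up from the day after start date until the first occurrence of the following endpoints". The list holds the first seizure record, age 85, cancer, alcohol-related disease, drug abuse and the end of the study. The synopsis adds death. Hospital admission is in neither list.

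Under section 4.5.1 a patient is "accepted as a case if the patient was referred to a consultant, and/or admitted to hospital for the event". The section then sorts seizures into acute symptomatic, unprovoked and unclassifiable. The first group is defined by closeness in time to a cause such as cerebrovascular disease, head injury or infection of the central nervous system: "Close temporal relationship to the seizure is defined as 1 week for the majority of events listed, with certain exceptions".

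**The concern.** Not knowing what a patient took in hospital is a reason to leave that patient out of a comparison of drug users with non-users. It is no reason to leave a real seizure out of a count of seizures. Because the rule is part of deciding who is a case, it acts on both objectives.

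The denominator is not cut to match. Section 4.5.1 also excludes alcohol-related seizures and seizures in cancer patients, but there section 4.4 ends follow-up at the corresponding diagnosis, so numerator and person-time agree. For admissions, the weeks afterwards stay in the denominator while the seizures that occur in them are discarded.

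At stake are the rate that answers objective 1, its age- and sex-specific versions, and the rates by epilepsy status. The mix of seizure types among accepted cases may shift as well, since several of the listed causes of acute symptomatic seizures often bring a patient into hospital before the seizure.

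**Working it through.** **1. The plan's own figure.** Section 4.9.1 assumes 100,000 person-years in each group and 50 seizures per 100,000, so 50 expected events per group. The upper 95% limit at an estimated ratio of 1 is exp(1.96 × √(1/50 + 1/50)) = exp(0.392) = 1.48, as stated. That figure concerns objective 2 and is not in dispute. The protocol has no corresponding figure for the incidence objective.

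**2. Direction.** Let N be the accepted seizures before the admission rule, D the number that the rule discards and T the person-years. The reported rate is (N − D)/T instead of N/T, so it can only be lower (or equal, if D = 0). Follow-up ends at the first seizure record, so a discarded patient cannot be counted later.

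**3. Could the denominator offset this?** Assume 0.05 to 0.2 admissions per person-year (not in the protocol) and remove 30 days after each. The share of person-time is 0.05 × 30/365.25 = 0.4% to 0.2 × 30/365.25 = 1.6%. Trimming the denominator would therefore recover little, and the result would be a rate outside post-admission periods, which is not what objective 1 asks for.

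**4. Illustrative size.** Inputs from section 2: "The incidence of acute symptomatic seizures has been estimated to be" 29–39 per 100,000 per year (A), and unprovoked seizures are put at 46–57 per 100,000 person-years (U). Assumed inputs: a share fa of acute symptomatic seizures and fu of unprovoked seizures with an admission in the prior month. Relative shortfall = (A·fa + U·fu)/(A + U).

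| A | U | A + U | fa = 10%, fu = 1% | fa = 50%, fu = 5% |
|---|---|---|---|---|
| 29 | 46 | 75 | 3.36/75 = 4.5% | 16.80/75 = 22.4% |
| 29 | 57 | 86 | 3.47/86 = 4.0% | 17.35/86 = 20.2% |
| 39 | 46 | 85 | 4.36/85 = 5.1% | 21.80/85 = 25.6% |
| 39 | 57 | 96 | 4.47/96 = 4.7% | 22.35/96 = 23.3% |

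The range is about 4% to 26%.

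**5. Which seizures are removed?** On the section 2 rates, acute symptomatic seizures are 29/86 = 34% to 39/85 = 46% of the total. If a prior admission is equally common before both types (fa = fu), they make up the same 34–46% of the removed cases. They become the majority only if fa/fu exceeds U/A, that is 46/39 = 1.2 to 57/29 = 2.0. Over fa = 10–50% and fu = 1–5%, their share of the removed cases runs from 2.9/(2.9 + 2.85) = 50% to 19.5/(19.5 + 0.46) = 98%. So the composition depends on shares that the protocol does not give.

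**The case against.** Three points can be made on the other side.

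*The incidence numerator is not spelled out.* Section 4.5 goes on to call everyone who meets the operational definition a potential case, and that definition in section 4.5.1 has no prior-admission condition. The analysis plan, not shown here, might use this wider group for incidence. The ambiguity is real, but it does not rescue the text: no section restores the excluded patients for objective 1. Nor is this a detail left open for the analysis plan, because the protocol places the exclusion in the outcome definition.

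*The removed cases are not acute symptomatic by definition.* A reader might infer from the one-week window that they largely are. The documents do not support this. The window only classifies seizures. The admission rule spans a month and any cause, so it also catches unprovoked and unclassifiable seizures. Conversely, where the seizure is part of the presentation (for example a first symptom of multiple sclerosis), there need be no earlier admission, and admission for the seizure itself is a route to becoming a case. This objection stands. What remains is a plausible inference that acute symptomatic seizures are hit harder.

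*The size is not in the protocol.* This stands too. The section 2 rates include the youngest ages, whereas the cohort is aged 20–84 and excludes cancer, alcohol-related disease and drug abuse. No share of seizures with a prior admission is given. It is tempting to suppose that half or all acute symptomatic seizures are lost, which would give 17–23% (half of 34–46%) or the full 34–46%. Nothing in the protocol supports either share, and the upper one is an extreme.

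**Conclusion.** The point holds in a limited form. Followed as written, section 4.5 discards true incident seizures from the only case set that the protocol defines, for a reason that bears on exposure alone, and leaves the matching person-time in place. The objective 1 rate is therefore biased downward. The direction follows from the text; the size does not. The 4–26% range is an illustration that rests on assumed admission shares (10–50% and 1–5%) and on background rates from other populations.

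That acute symptomatic seizures bear more of the loss is likely but inferred. A reader might go further and expect the shortfall to be greatest in older patients, since section 2 names the elderly among the groups in which acute symptomatic seizures predominate. The protocol has no admission figures by age, so that cannot be claimed. The change should be made: a stated objective is affected and the remedy is cheap.

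**What to change.** State in sections 4.5 and 4.9 that the prior-month admission exclusion applies only to the nested case-control analysis. Apply it there to controls as well as cases. Section 4.6 has no such rule for controls, so cases would come only from time without a recent admission while controls are sampled from all follow-up.

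For objective 1, compute incidence overall, by age and sex, and by epilepsy status from all accepted seizures, including patients admitted in the prior month. Report how many cases the exclusion removes.

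The cost is mainly wording. The affected profiles are already found and reviewed under section 4.5, and section 4.7 already collects hospitalizations in the year before the index date, so the rule can be applied to controls without a new data source.
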